Sample Size: Keeping in mind factors related to pilot trial feasibility, our target sample size ($n=60$; 30 LM-DA and 30 control) was chosen to allow detection of a 35% difference between the LM-DA and control arms for the primary measure (DCS score <25 ; Table 2). In a prior small study, 62% of parents of at-risk youth who received LMC reduced home

Table 5. Sample Size Estimates			
Control	LM-DA	% with DCS <25	Total Detectable sample size
		0.6	64
0.5	0.8	0.3	78
	0.85	0.35	54
	0.9	0.4	40
	0.6	0.3	84
	0.65	0.35	62
	0.7	0.4	48
0.3	0.5	0.3	78
	0.55	0.35	58
80% power, $\alpha=0.05$			

access to firearms, compared to 0% of those who did not receive LMC.⁴⁹ Estimates for the effect of LMC on behavior among adults with suicide risk do not exist, so our assumption of a 35% difference is conservative (prior work with other DAs has found an effect size of 40-80% on DCS between groups⁹²). While this sample size will not allow for full power to analyze moderators by site (as related to either LM decision or trial feasibility measures), it should generate adequate pilot information concerning site selection for the subsequent trial.

B. Description of Population to be Enrolled: We will enroll three populations:

- a. 60 patients seen in the ED for SI/SA
- b. Up to 60 influential adult family members or friends (one per enrolled patient), either in person or by telephone (if not present in the ED; n=60 total). Enrollment of a family member or friend will not be required for a patient to participate.
- c. 100 emergency department providers for surveys and 20 for qualitative interviews (may participate in survey, interview or both)

Table 3. Inclusion/Exclusion Criteria

[figure not shown]
	Inclusion	Exclusion
Patients (n=60)	
 • Being evaluated in the emergency department for SI/SA. • Deemed medically stable by ED physician • Age ≥ 18 years • Able and willing to have telephone follow up at 1 week • Report ≥ 1 firearm at home 	
 • Unable to participate medically or cognitively (e.g. sustained altered level of consciousness, hostility, psychosis, sexual assault victim, severe vomiting or pain) • Currently in legal custody • Live in group home or other supervised custody • Already enrolled
Family member or friend (n=60)	
 • Age ≥ 18 years 	
 • Unable to participate cognitively • Already enrolled • Currently in legal custody

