ED Providers (n=100)	
 • Physicians, physician extenders (i.e., physician assistants or nurse practitioners), nurses, and behavioral health evaluators (e.g., social workers, psychologists, advanced practice nurses) who work in the participating EDs • Cared for ≥ 1 participating patient • Completed current care of participating patient(s) prior to beginning the survey 	
 • Current or former member of the study team (i.e. PI, CO-I, RA)

C. Study Design and Research Methods: In this pilot randomized controlled trial, we will test the LM-DA in a sample of 60 adult patients being evaluated for suicide risk at three large hospital EDs. Thirty nine patients will be randomized to the LM-DA group, while 21 will be randomized to the control group (13/7 at each site). Figure 2 displays the overall study flow. Analysis and reporting will follow CONSORT guidelines, and we will register the trial on clinicaltrials.gov. Family member or friends who are concurrently enrolled will also be enrolled in the ED, in the same randomization group as the patient. ED Providers will be surveyed separately.

Study Sites: To prepare for the subsequent multi-site trial, including by identification of moderators of LM-DA and study feasibility at different sites, the pilot will recruit patients, family members/friends, and providers from the EDs at three large, diverse Colorado Hospitals: (1) University of Colorado Hospital (tertiary care center without dedicated psychiatric ED; suburban Denver; part of UCHealth consortium); (2) Memorial Hospital

(hospital with dedicated psychiatric ED; draws from large catchment area in southern Colorado, including rural and urban populations; high firearm ownership rate; part of UCHealth consortium); and (3) Denver Health Medical Center.

Figure 2. General Study Flow

Enrollment:

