- ED Providers: Provider survey invitations will be emailed and will include a unique link to complete a REDCap online survey. To supplement these survey data, we will conduct qualitative interviews with 20 ED providers to further explore LM-DA acceptability, feasibility of real-world implementation, and training. All providers who are a part of a patient –subject’s clinical team will be invited by email to participate in the initial survey. At the end of the survey, there will be an invitation to participate in a follow-up qualitative interview. Interested providers will be instructed to email or call the study team, as their name will not be on the survey. If more providers opt for qualitative surveys than anticipated, we will select a sample to optimize balance across provider groups and sites.
- All participants will receive a gift card as an incentive (\$25 for patients; \$10 for family or friends; \$5 for providers who complete the online survey; \$15 for providers who complete a qualitative interview for a total incentive of \$20).

Randomization:

- Patients: At each ED, enrolled patients will be randomly assigned to the LM-DA or control arm (Figure 2). To reduce bias and achieve balance among arms, we will randomize patients in blocks.⁹⁰
- Family members/friends: If a family member or friend is concurrently enrolled, they will be automatically randomized into the same arm as the patient, as they will potentially be reviewing the LM-DA with the patient and assisting with decision making.
- ED Providers: Providers will be asked to provide answers to a survey after the patient’s visit. Thus, they are not randomized, nor can they feasibly be blinded given their ongoing care relationship with patients during the study.

Baseline Measurements & Intervention:

- Patients: The RA will give the patient a study tablet with an introductory short survey and basic information about suicide prevention. In the intervention arm only, patients will then complete the LM-DA on the tablet. All patients in both arms will answer questions about their ED care and their anticipated care plan (including knowledge about the rationale for reducing access to firearms as a safety measure, and their intent to decrease access to firearms at home). Study participation will not affect clinical care, including discharge or admission planning.

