Loss of confidentiality (all participants): Loss of confidentiality is a potential serious risk. We will be diligent in safeguarding protected health and other participant information in the collection, processing, and storage of information, and all the data generated by the study will be kept strictly confidential. No reports will be released containing protected health information or other identifiers that would allow a study participant to be identified. Individual participant contact information will be collected at the time of enrollment (prior to randomization) and this information will be kept in a secure, locked file cabinet in the Department of Emergency Medicine offices and in password protected, secure electronic files. Participants will not be identified by name or medical record number on any of the data forms or specimens except the initial enrollment and consent forms. Other paper and electronic data will be made anonymous using unique identification codes and participant initials. Electronic files will be stored on password protected computers, or REDCap, behind the University of Colorado Denver firewall.

Worry about firearm confiscation

- Patients and family members/friends: We recognize that participants may view this as a study risk, although it is not actually one. Specifically, some may fear that, if they reveal they have firearms at home, legal authorities will confiscate them. We will explain to every participant that study staff will not enter information about firearm access into the medical record, nor will they disclose access to any legal authorities. We will also not ask about how firearms were acquired (i.e., whether they were legally-purchased or transferred).

[figure not shown]
Should staff have concern about a participant's imminent safety, they would follow study protocols to notify clinical staff in the ED or connect the patient with a suicide hotline. While clinical staff may document firearm access, as they might during typical care, we will reassure participants that such information is not shared with legal authorities unless an individual is specifically threatening harm towards specific individuals (as per required reporting under the *Tarasoff* decision).

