
Another area of challenge is blinding to treatment arm. RAs will carry out all study procedures

Figure 3. Time Spent in ED by a Patient with SI/SA

but cannot feasibly be blinded to study arm, as they will need to ensure the patient can access the LM-DA. To blind patients, we plan to use deception (with IRB approval) in the informed consent process such that patients know

the study is examining ways to enhance safety of suicidal patients but do not know that the LM-DA is the intervention of interest. ED providers will not be blinded to participant study group, as providers may review the LM-DA printed results with patients (as they would in real-world implementation). We will notify providers of the study at the start of enrollment and explain the purpose, with the request that providers continue to provide usual care (with or without LMC, as per their usual practice) for patients in the intervention and control groups. A third challenge is testing the role of family or friends. Not all suicidal patients have someone present with them in the ED, so there will be real-world variability in how family or friends are involved with DA completion. Ideally, the person with decision-making control over firearm storage would be involved, but may not be present with the patient. In the current proposal, we will record how often family or friends are present and are (or are not) the ones with control of firearm storage. We will also record how often they are willing to participate in the study – all of these findings will help lay the groundwork for future study. If we find any aspects of the LM-DA are unacceptable, we will revise those aspects and re-review with stakeholders prior to future implementation. Another limitation is finding differences across sites, but not enough events to adjust for site (with a fixed effect). In this case, given that this is a pilot study, we will use two strategies: (1) ignore site and summarize the overall results, and (2) analyze the results ignoring the site with few events. A future study will allow to account for differences across sites.

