F. Data Analysis Plan: We will describe the three sites in terms of patient demographics as well as the primary measure (DCS score <25) using appropriate statistical tests (e.g. anova, chi-square). If no differences are found between the three sites, we will ignore site and compare the proportion of the primary measure in the control and intervention groups as the primary analysis. If differences are found among sites and there are enough events, we will use a logistic regression model with a fixed effect for site and with a treatment indicator as the main predictor. Missing data for the primary measure should be minimal, given that this will be obtained before patients leave the ED. For secondary measures, we will use descriptive statistics including proportions with 95% confidence intervals for knowledge, acceptability and feasibility; whether the criteria in Table 1 have been met will be based on the confidence intervals of the proportions. Keeping in mind factors related to pilot trial feasibility, our target sample size (n=60; 30 LM-DA and 30 control) was chosen to allow detection of a 30% difference between the LM-DA and control arms for the primary measure (DCS score <25; Table 2) While this sample size will not allow for full power to analyze moderators by site (as related to either LM decision or trial feasibility measures), it should generate adequate pilot information concerning site selection for the subsequent trial. Participants and RAs will enter survey data directly into REDCap. Participants completing REDCap surveys will be sent a unique link for participation. For follow-up calls, chart reviews and other documents, RAs will enter data into REDCap or store it on password-protected university servers. We will export data to SAS for analyses.

G. Summarize Knowledge to be Gained: The proposed research will provide the scientific foundation for improvement and examination of real-word implementation of an effective, patient-centered LM-DA in EDs and other settings. A web-based tool offers the potential to significantly enhance current care, decrease real-world access to lethal means of suicide, and thereby decrease short-term risk of suicide.

H. References:

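### An exact 13/7 count per site lets unblinded recruiters foresee about two final assignments at each site, and the text does not secure the introductory survey before assignment

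*Combined protocol and SAP*

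**What the plan says.** **Allocation.** Section IV.C gives 39 LM-DA and 21 control patients in total, and states the split at site level: "21 will be randomized to the control group (13/7 at each site".

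**Method.** The Randomization paragraph says "At each ED, enrolled patients will be randomly assigned to the LM-DA or control arm (Figure 2" and "To reduce bias and achieve balance among arms, we will randomize patients in blocks". The text gives no block size, no variation in block size, no holder of the sequence and no means of concealment.

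**Who recruits and who knows the arm.** Under Enrollment, RAs find patients on the tracking board, consult the treating physician, approach the patient and assess the remaining eligibility criteria. Section E says that RAs carry out every study procedure "but cannot feasibly be blinded to study arm, as they will need to ensure the patient can access the LM-DA".

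**Order of steps.** Section IV.C runs Enrollment, Randomization, then Baseline Measurements & Intervention. The introductory tablet survey is under the last of these, ahead of the LM-DA. The confidentiality paragraph times one item explicitly: "Individual participant contact information will be collected at the time of enrollment (prior to randomization". The paragraph on suicidal ideation or behavior places the baseline C-SSRS at enrollment, and nomination of a family member or friend is described under Enrollment. Figure 2, the study flow, is not visible in the text available.

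**A conflicting allocation.** The Sample Size paragraph has "30 LM-DA and 30 control) was chosen to allow detection of a 35% difference between the LM-DA and control arms". The Data Analysis Plan (F) repeats 30 and 30 but with a different effect: it "was chosen to allow detection of a 30% difference between the LM-DA and control arms for the primary measure".

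**The concern.** RAs probably have to know the arm after assignment. They do not have to be able to foresee it. An exact count at each site, known to the people who recruit there, makes the end of each site's sequence foreseeable whatever the block scheme.

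The RA has room to act on that knowledge, even without meaning to. The approach is timed within a stretch of ED care that may last minutes to hours, and one site reports an average psychiatric stay of about 23 hours. Some exclusions in Table 3, such as hostility or being cognitively unable to take part, call for judgement.

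The primary measure (DCS below 25) is self-reported in the ED. With 21 controls, one patient moves the control proportion by 1/21 = 4.8 percentage points. With 39 in the LM-DA arm, one patient moves it by 1/39 = 2.6 points. A few selectively timed approaches could therefore be visible in the result.

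On timing, the baseline questionnaire covers home firearms, and firearm storage at follow-up is to be compared with baseline and is meant to become a primary measure of the larger trial. A baseline taken before anyone knows the arm is safer than one that may be taken afterwards.

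**Working it through.** **1. The plan's own figure.** 3 × 13 = 39 and 3 × 7 = 21, total 60. The stated totals follow from 13/7 at three sites.

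**2. Certain assignments under an exact count.** Once one arm is used up, every remaining assignment is certain. In a random ordering of *a* LM-DA and *b* control assignments, the expected number left after the last control is a/(b+1), and after the last LM-DA it is b/(a+1). So

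E(certain) = a/(b+1) + b/(a+1).

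For one block of 13/7: 13/8 + 7/14 = 1.625 + 0.500 = 2.125 of 20 (10.6%). Over three sites: 3 × 2.125 = 6.4 of 60, made up of 3 × 1.625 = 4.9 LM-DA and 3 × 0.5 = 1.5 control.

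**3. Hidden mixed blocks that still total 13/7.** Blocks of 4/2, 4/2 and 5/3 in random order give 13/7. If the sizes are hidden, an RA with a tally can be certain only about the closing run of the site's sequence, which lies inside the last block:

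- last block 4/2: 4/3 + 2/5 = 1.73
- last block 5/3: 5/4 + 3/6 = 1.75

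That is about 1.7 per site, or 3 × 1.73 = 5.2 of 60. Hiding the blocks removes little of the certainty that comes from the exact count.

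**4. What would make it worse.** 13 and 7 share no common factor, so equal blocks smaller than 20 cannot produce 13/7. The rows below the first are hypothetical. They use unequal blocks that sum to 13/7 and assume that the RA knows their sizes and order.

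| Blocks at a site | Certain of 20 | Best guess correct |
|---|---|---|
| one 13/7 | 2.1 (10.6%) | 68.9% |
| two 6/3, one 1/1 | 4.9 (24.3%) | 73.0% |
| three 4/2, one 1/1 | 6.2 (31.0%) | 74.5% |
| six 2/1, one 1/1 | 9.0 (45.0%) | 77.5% |

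The best guess always names the arm with more assignments left in the block. Its reference value is 13/20 = 65%, the success rate of always guessing LM-DA. With one block of 20 the gain is 68.9 − 65 = 3.9 points.

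**5. If 30/30 governs instead.** Taking 10/10 per site as an assumption, one block gives 10/11 + 10/11 = 1.8 of 20, or 5.5 of 60. The conclusion does not depend on which allocation is kept, provided an exact count per site is fixed.

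**6. Timing, item by item.**

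| Item | Where the text puts it |
|---|---|
| Contact details | at enrollment, explicitly before randomisation |
| Having a firearm at home | eligibility question, at screening |
| Baseline C-SSRS | at enrollment |
| Family or friend nomination | described under Enrollment |
| Introductory tablet survey | under the heading that follows Randomization, before the LM-DA |

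Only the introductory survey is listed after randomisation, and nothing states that the assignment is withheld until it is submitted.

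**The case against.** The strongest reply is that silence on concealment does not show that RAs hold or can deduce the list. There are also partial safeguards. The stated aim is to approach every patient who may be eligible, and the treating physician is asked about medical stability. Reasons for non-participation are recorded, so selective skipping could be examined. Patients are not told that the LM-DA is the intervention under study. This stands as far as it goes, but these measures would help detect or dilute selection. They do not prevent the closing assignments from being known.

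A reader might infer that a quarter to nearly half of assignments are predictable. The documents do not support that. Those figures need small blocks of known size, and no block size is given. With one block of 20, guessing beats the trivial 65% by only about 4 points, so the exposure is chiefly the closing run at each site.

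A reader might also infer from the heading order that baseline as a whole is taken with the arm known. That is not established either. The C-SSRS is placed at enrollment, nomination of a companion is described under Enrollment, and firearm presence is asked at screening. The sentence on contact details belongs to a confidentiality paragraph and does not say that nothing else precedes randomisation. Figure 2 might settle the sequence but cannot be seen.

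**Conclusion.** The point holds in a limited form. Under an exact 13/7 per site, an RA who knows the target and can tally all assignments at that site would know about 1.7 to 2.1 final assignments for certain, roughly 5 to 6 of 60 overall. That RAs know the target and keep such a tally is an assumption, though an easy one to meet. The resulting bias in the primary comparison cannot be sized from the documents.

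On timing, the text permits the introductory survey to be given with the arm known to the RA and does not exclude it. It does not show that this will happen.

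A fixed count is not an error in itself. This is a cheap improvement, worth making because the pilot is a rehearsal for a larger trial.

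**What to change.** 1. Reconcile 39/21 in section IV.C with 30/30 in the Sample Size paragraph and in section F, since the allocation ratio has to be settled first.
2. Replace the exact count at each site with an overall allocation ratio and approximate site totals. This is the step that removes the certain closing assignments.
3. Generate a sequence stratified by site with randomly varied block sizes hidden from RAs. REDCap, already the data system, is one route; any central method with the same properties would serve.
4. State that the assignment is released only after consent, the baseline C-SSRS and the introductory survey have been submitted, immediately before the LM-DA step. The LM-DA already follows that survey, so the patient's sequence need not change.

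The cost is minor configuration work, a few sentences in the protocol, and a site split that may differ from target by one or two patients.

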Knowledge	Questions about suicide and LM	X	X				60% of patients identify firearm access as risk for suicide
Decision conflict	Decisional Conflict Scale (DCS)	X	X				Effect size 0.3-0.4 after intervention (target score <25)
Values concordance	DCS Values Clarity subscale	X					NA (informs next trial)
Behavior intent	Theory of Planned Behavior	X					NA (informs next trial)
SHORT-TERM							
Firearm access	Self-report	X	X				NA (informs next trial)
LONG-TERM							
Suicide attempts, deaths	Self-report C-SSRS (BL, 1 week); medical record review (BL, 1 & 3 months)	X	X	X	X		Able to review records for 85% of participating patients
TRIAL MEASURES							
Feasibility	Eligibility, participation Phone follow-up Suicide outcome ascertainment	X		X	X		>50% participation >75% completion Able to review records for 85% of participating patients
Provider training	Time to complete; user feedback					X	NA (informs next trial)
ADDITIONAL MEASURES							
Demographic and clinical characteristics	Questionnaire, C-SSRS; medical record review	X		X	X		NA (informs next trial)
Healthcare utilization review	Medical record review			X	X		Able to review records for 85% of participating patients

estimates decisional uncertainty through personal perceptions of issues such as uncertainty in choosing options, modifiable factors contributing to uncertainty, and effective decision making (e.g., expressing satisfaction with the choice). The DCS is a 16-item scale (with Likert scale response options) that has high reliability and test-retest correlation (Cronbach's alpha coefficients > 0.78).⁹² In prior work, the DCS has been shown to discriminate between known groups who make or delay decisions (effect size 0.4-0.8).⁹² Scores less than 25 (out of 100 total) are associated with implementing decisions;⁹² we will use this threshold as one criterion for progression to the next trial (Table 1), as [name] has done in other studies.

- **Values Concordance:** We will use the "Values Clarity"⁹² subscale of the DCA to examine how much participants feel their decisions are in line with their values.
- **Behavior Intent:** We will measure self-reported intent to reduce access to firearms, including the chosen option(s) for storage, using a Theory of Planned Behavior questionnaire scale.⁹³

(3) Short-Term Outcome: At phone follow-up, we will assess firearm storage (to identify changes from baseline). This will be a primary measure for the subsequent, larger trial.

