(4) Long-Term Outcome: This pilot is not powered to detect change in suicide death rates (the outcome most likely affected by lethal means safety). We will assess suicidal behavior at phone follow-up (self-report of SI/SA) using the "since last visit" C-SSRS,⁹¹ as well as via structured review of electronic medical records (ED visits for SI/SA) and vital statistics (deaths) at 1 and 3 months.

(5) Trial Feasibility Outcomes:

- **Eligibility and participation rates:** We will record demographic information (gender, age group, race/ethnicity) and reasons for non-eligibility or non-participation for patients not enrolled in this pilot trial to inform our planned trial. We will also record participant disposition (discharge home versus hospitalization) and how often participants have a family member or friend present in the ED (with willingness of companion to participate). We will analyze these data for each of the clinical sites.
- **Follow-up rates:** We will record rates for telephone follow-up at 1-week.
- **Suicide composite measure:** We will record the feasibility of accessing medical records and vital statistics.
- **Provider training:** Measures will include estimated training time required for competence (an important feasibility measure for future implementation) as well as user feedback about the training itself.

Analysis: We will describe the three sites in terms of demographics as well as the primary measure (DCS score <25) using appropriate statistical tests (e.g. anova, chi-square). If no differences are found between the three sites, we will ignore site and compare the proportion of the primary measure in the control and intervention groups as the primary analysis. If differences are found among sites and there are enough events, we will use a logistic regression model with a fixed effect for site and with a treatment indicator as the main predictor. Missing data for the primary measure should be minimal, given that this will be obtained before patients leave the ED. For secondary measures, we will use descriptive statistics including proportions with 95% confidence intervals for knowledge, acceptability and feasibility; whether the criteria in Table 1 have been met will be based on the confidence intervals of the proportions.

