At follow up, if a participant expresses suicidal ideation or appears at risk to themselves or others, the RA will connect the participant via 3-way call with Colorado Crisis Services (the free state hotline, staffed 24/7 with trained counselors). In the event the participant refuses to speak with the crisis line or the call is prematurely terminated, research staff will follow HIPAA clinical guidelines outlined for healthcare providers and the privacy rule in the event a person poses a serious or imminent threat to themselves or others. Under these circumstances, the Privacy Rule allows health care providers to disclose necessary information to law enforcement, family members of the patient, or other persons. If outside assistance is required due to imminent risk, the research staff may have to report the current risk level and location of the participant, though the nature of the study will be kept confidential.

In this pilot, we will enroll patients regardless of admission or discharge status to examine

feasibility of a larger trial and real-world application. We will also enroll patients regardless of their patient status, i.e. placed on a Colorado M1 hold (more commonly referred to as a “mental health hold”). Per the State of Colorado, A M1 hold is indicated when a patient poses an imminent threat to themselves or others, or, is gravely disabled due to mental illness. As part of the M1 hold process, a patient has specific rights (covered in Colorado form M2). Voluntary participation in a research study does not contradict or violate these specific patient rights. A patient on a M1 hold may accept or decline participation in the research study. This will specifically be communicated as part of the consent process to reduce coercion.

Participating in this research study will not offer protection from future SI, future SA, future suicidal behaviors or future self-harm. As such, this will be communicated to both patient and family member/friend participants during consent.

Coercion (all participants): Because some study investigators are also affiliated with the clinical sites, there is the potential risk of coercion.

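### The reason given for unblinded research assistants covers only the ED session, but they also conduct and record the 1-week call, with no masked caller planned

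*Combined protocol and SAP*

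**What the plan says.** Section IV.E (Potential Scientific Problems) states that "RAs will carry out all study procedures" and continues, in the same sentence, "but cannot feasibly be blinded to study arm, as they will need to ensure the patient can access the LM-DA". This is the only reason given for leaving RAs unblinded. The same section describes masking of patients through deception at consent: they know that the study concerns safety but not that the LM-DA is the intervention under test.

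Section IV.C, under Baseline Measurements & Intervention, places LM-DA use in the ED: "In the intervention arm only, patients will then complete the LM-DA on the tablet". It also has research staff enter the LM-DA results, including the plan for reducing firearm access, into the patient's REDCap file.

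The 1-week call supplies two outcomes. Section IV.A(3) says: "At phone follow-up, we will assess firearm storage (to identify changes from baseline"), and adds: "This will be a primary measure for the subsequent, larger trial". Section IV.A(4) says: "We will assess suicidal behavior at phone follow-up (self-report of SI/SA"), using the since-last-visit form of the C-SSRS.

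Two places put RAs on that call. The risk section, on what happens if a participant is at risk at follow-up, says that "the RA will connect the participant via 3-way call with Colorado Crisis Services". Section IV.F (Data Analysis Plan) says: "For follow-up calls, chart reviews and other documents, RAs will enter data into REDCap".

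**The concern.** Giving a patient access to a tablet-based decision aid explains why the person in the ED must know the arm. It does not explain why the person who telephones a week later must know it. Both outcomes taken on the call are self-reports given to an interviewer, and Section IV.E itself recognises that firearm disclosure is sensitive and depends on how staff approach it. An interviewer who knows the arm, and may have seen the storage plan in REDCap, could probe or code reported change differently between arms without meaning to.

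At stake is the credibility of the between-arm storage estimate. The pilot attaches no progression threshold to it, but Table 1 says that it informs the next trial, where storage is to be a primary measure. A bias of this kind does not shrink as the sample grows. The pilot is also the natural place to learn whether masked calling is workable.

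**Working it through.** No figure in the plan depends on this point, so the main check is to set the passages side by side.

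**1. Scope of the reason.** The reason is access to the LM-DA (IV.E). The LM-DA is completed on the study tablet during the baseline session (IV.C). Nothing describes LM-DA access during the call. The reason therefore covers the ED session only.

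**2. Who is on the call.** RAs carry out all procedures (IV.E), an RA is on the line if a crisis referral is needed (risk section), and RAs enter the follow-up data (IV.F). No section names a masked caller, restricts what the caller may see in REDCap, or says why masking the call is infeasible.

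**3. Which outcomes are exposed.** Firearm storage and the C-SSRS are taken by telephone. Table 1 also appears to mark knowledge, the DCS and the Ottawa Acceptability Scale at 1 week. The Ottawa scale is for the LM-DA group only, so asking it early would reveal the arm.

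**4. What is not exposed.** The primary measure, DCS below 25, is obtained before the patient leaves the ED (IV.A Analysis; IV.F). The call cannot affect that comparison.

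**5. Illustration of size.** All bias values here are assumptions; the documents give none.

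- *Miscoding.* Suppose 30% truly change storage in each arm and 15% of LM-DA non-changers are recorded as changed. The LM-DA arm reads 0.30 + 0.70 × 0.15 = 0.405 against 0.30, a spurious 10.5 points.
- *Pilot precision.* Take the 39/21 allocation in IV.C (the sample-size text says 30/30, a separate matter) and 75% follow-up, near the Table 1 threshold: 0.75 × 39 = 29.25, about 29, and 0.75 × 21 = 15.75, about 16. The 95% half-width is 1.96 × √[p(1−p)(1/16 + 1/29)]. It is 0.28 at p = 0.30 and 0.305 at p = 0.50, so 28 to 31 points.
- *False-positive rate.* Suppose there is no true effect, the base rate is 30% to 50%, and reporting favours LM-DA by d points. For a two-sided 5% test, P(reject) = Φ[(d − 1.96·se₀)/se₁] + Φ[(−d − 1.96·se₀)/se₁], where se₀ is the pooled and se₁ the unpooled standard error.

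| d | 39/21 | about 29/16 | 200 per arm (assumed) |
|---|---|---|---|
| 5 points | about 7% | about 6% | 17–19% |
| 10 points | 11–12% | about 10% | 52–56% |
| 15 points | about 20% | 16–17% | 86–88% |

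Worked entry, 200 per arm, 30% against 40%: se₀ = √(0.35 × 0.65 × 2/200) = 0.0477; se₁ = √(0.21/200 + 0.24/200) = 0.0474; (0.10 − 1.96 × 0.0477)/0.0474 = 0.14, giving about 0.555.

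The plan specifies no between-arm test of storage in the pilot, so the first two columns show scale only. The last column shows why the procedure matters if it is carried forward.

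**The case against.** The best defence is that nothing decided in this pilot rests on the exposed data. Storage and suicide outcomes are labelled exploratory, and storage has no progression threshold. The larger trial will have its own protocol and can set its own assessor masking; the documents do not say that the pilot's storage estimate will size it. With a half-width of 28 to 31 points, a bias of about 10 points would be hard to see here. Suicidal behaviour is also ascertained from medical records and deaths from vital statistics, not from the call alone. All of this stands and limits the importance of the point.

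A second defence is rapport. Section IV.E relies on it for honest firearm disclosure, and telephone completion above 75% is a progression criterion. This carries less weight, because the plan never promises that the patient will hear a familiar voice.

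A reader might infer more than the text supports in three ways:

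- *That the same individual who ran the ED session makes the call.* The documents identify a role. They allow the same person to call but do not require it.
- *That the RA helped make the storage plan, so the patient will want to please that person.* Patients complete the LM-DA themselves, with family or friends if they wish; research staff are described only as entering the results. Masking at consent also reduces, without removing, the scope for patients to report what they think the study wants. It does not mask the interviewer.
- *That a masked caller is certainly available without added staff.* The number of RAs is not stated.

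**Conclusion.** The concern holds as a gap in justification and procedure. The single reason for unblinded RAs applies to the ED session, while RAs also conduct and record the 1-week call with no masking and no separate reason. The documents do not support a reading that the pilot's primary result is biased, since DCS below 25 is collected before the call takes place.

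The effect is confined to exploratory outcomes in this trial. It matters mainly through firearm storage, because of that measure's planned role in the larger trial. Its size cannot be estimated from the documents. How far coding could be influenced also depends on whether the storage items are closed or probed, which is not stated. The 10.5-point figure and the table of rejection rates rest wholly on assumed reporting differences. This is a cheap improvement worth making, not an obstacle to running the pilot.

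**What to change.** - In Section IV.E, limit the statement to the ED session: RAs are unblinded there because they must provide access to the LM-DA.
- Where staffing allows, have the 1-week call made by an existing RA who did not run that patient's ED session.
- In REDCap, hide from the caller both the allocation field and the LM-DA results with the storage plan. Hiding allocation alone would leave the arm evident.
- Use a scripted interview with storage and C-SSRS items first. Reveal the LM-DA-only acceptability items at the end, so that the form does not disclose the arm earlier.
- Record whether, and at what point, the caller became aware of the arm, and report unmasked calls as a limitation. The proportion of calls that stay masked is itself useful feasibility information for the next trial.
- Leave the safety procedures on the call as written. They respond to what the participant says and do not refer to the arm.

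The cost is scheduling effort for at most 60 patient calls and a change to REDCap access rights. The downsides are some possible loss of rapport and some callers unmasked by the conversation. That this can be done without added staff is an assumption.
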